	
Serious Adverse Events (SAEs) (Amended, 23 November 2020)
 
 – Occurrence and relationship to vaccination of SAEs from Day 1 up to 30 days post last vaccination. – Occurrence and relationship to vaccination of SAEs from Day 1 up to 12 months post last vaccination. – Occurrence of SAEs related to study vaccine, from Day 1 up to end of study. – Occurrence of SAEs related to study participation or to GlaxoSmithKline concomitant medication/vaccine during the entire study period. – Occurrence and relationship to vaccination of fatal SAEs from Day 1 up to 30 days post last vaccination. – Occurrence and relationship to vaccination of fatal SAEs from Day 1 up to 12 months post last vaccination. – Occurrence of related-fatal SAEs from Day 1 up to end of study. 
pIMDs (Amended, 23 November 2020)
 
 – Occurrence and relationship to vaccination of pIMDs from Day 1 up to 30 days post last vaccination. – Occurrence and relationship to vaccination of pIMDs from Day 1 up to 12 months post last vaccination. – Occurrence of related serious pIMDs after 12 months post last vaccination up to study end.

Exploratory

CCI

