8.5.1. Safety definitions

Please refer to Section [12.5](#) for safety definitions.

8.5.2. Time period and frequency for collecting AE and serious adverse event (SAE) information

An overview of the protocol-required reporting periods for safety outcomes is given in **Table 19**. Refer to the Section [12.5.8.1](#) for details on the time period for recording safety information.

Table 19 Reporting periods for collecting safety information (Amended, 23 November 2020)

Events	Dose 1 (Visit 1)	7 days Post first Dose	30 days Post first Dose	Dose 2 (Visit 2)	7 days Post last vaccination	30 days Post last vaccination (Visit 3)	One year Post last vaccination	Monthly contact until study end*
	Day 1			Month 2		Month 3	Month 14	
Timing of reporting	Day 1	Day 7	Day 30		Day 61	Day 67	Day 91	
Solicited AEs								
Unsolicited AEs (including cellulitis)								
Medically attended visits								
AEs/SAEs leading to withdrawal from the study								
All SAEs								
SAEs related to the study vaccine								
SAEs related to study participation or concurrent GlaxoSmithKline medication/vaccine ^a								
pIMDs ^b								
Pregnancies ^d								
HZ episodes								

AE= Adverse event; HZ= Herpes Zoster; pIMDs= potential immune mediated diseases; SAE= serious adverse event

Note: For each solicited and unsolicited AEs the subject experiences, the subject will be asked if he/she received medical attention defined as hospitalization, an emergency room visit or a visit to or from medical personnel (medical doctor) for any reason and this information will be recorded in the eCRF.

^a SAEs related to study participation or **GlaxoSmithKline** concomitant medication/vaccine are to be recorded from the time the subject consents to participate in the study. All other SAEs are to be reported after administration of the first dose of vaccine.

^b *All pIMDs are to be reported up to 12 months post last vaccination. Beyond this time period, only related SAEs (including related serious pIMDs as per investigator assessment) are to be reported.*

^δ This applies to pregnancy cases with exposure to **the study treatment** at any age of gestation. The timing of exposure to **the study treatment** during pregnancy is estimated in relation to the first day of the last menstrual period, ultrasound or known date of fertilization (e.g., assisted reproductive technology).

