	
The percentage of subjects with at least 1 report of unsolicited AE (including cellulitis) classified by MedDRA and reported within 30 days (Days 1-30) post-vaccination period will be tabulated with exact 95% CI. The same tabulation will be performed for grade 3 unsolicited AEs, for unsolicited AEs with a relationship to vaccination, grade 3 unsolicited AEs with a relationship to vaccination.
 
Number and percentage of any, grade 3, related, grade 3 related and medically-attended adverse events reported within 30 days (Days 1-30) post-vaccination period according to MedDRA primary preferred terms.
 
Number and percentage of SAEs from first vaccination up to 12 months post last vaccination will be presented with 95% CI. The same tabulation will also be done for the interval starting from first vaccination up to 30 days post last vaccination.
 
Number and percentage of SAEs causally related to vaccination for the interval starting from first vaccination up to 30 days post last vaccination and from first vaccination up to 12 months post last vaccination and from study start up to study end will be presented with 95% CI.
 
Number and percentage of subjects experiencing fatal SAEs, classified by MedDRA Primary System Organ Class and Preferred Term will be tabulated using date of onset of SAE for the time periods—from first vaccination up to 30 days post last vaccination and first vaccination up to 12 months post last vaccination and from study start up to study end will be presented with 95% CI. Fatal SAEs will also be tabulated using the date of death within the same time periods.
 
Number and percentage of fatal SAEs causally related to vaccination for the interval— starting from first vaccination up to 30 days post last vaccination and from first vaccination up to 12 months post last vaccination and from study start up to study end will be presented with 95% CI.
 
Number and percentage of pIMDs from first vaccination up to 12 months post last vaccination will be presented with 95% CI. The same tabulation will also be done for the interval, starting from first vaccination up to 30 days post last vaccination.
 
Number and percentage of pIMDs causally related to vaccination from first vaccination up to 12 months post last vaccination will be presented with 95% CI. The same tabulation will also be done for the interval starting from first vaccination up to 30 days post last vaccination and, for serious pIMDs causally related to vaccination, after 12 months post last vaccination up to study end. (Amended, 23 November 2020)
 
The proportion of subjects with concomitant medication will be tabulated, within 30 days post vaccination and overall, with exact 95% CI.
 
Listing of fatal SAEs, SAEs, pIMDs and withdrawals (from the study or from vaccination) due to AEs, SAEs, solicited and unsolicited AEs will be generated for corresponding follow-up period. Listing of pregnancy during the entire study period will be generated. Listing for all the suspected HZ episodes will be generated.

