12.5.8. Detecting and recording adverse events, serious adverse events and pregnancies

A Paper Diary (pDiary) hereafter referred to as Subject Diary will be used in this study to capture solicited AEs and unsolicited AEs. The subject should be trained on how and when to complete each field of the Subject Diary.

The subjects/subject's LAR (s) will be instructed to contact the investigator immediately should the subjects manifest any signs or symptoms they perceive as serious.

Subject Diary training should be directed at the individual(s) who will perform the measurements of adverse events and who will enter the information into the Subject Diary. If a person other than the subject/subject's/LAR(s) enters information into the Subject Diary, this person's identity must be documented in the Subject Diary. Any individual that makes entries into the Subject Diary must receive training on completion of the Subject Diary at the time of the visit when Subject Diary is dispensed. This training must be documented in the subject's source record.

At each vaccination visit, diary cards will be provided to the subject. The subject will be instructed to measure and record the axillary body temperature, any solicited local/general AEs (i.e. on the day of vaccination and during the next 6 days) or any unsolicited AEs (i.e. on the day of vaccination and during the next 30 days occurring after vaccination. The subject will be instructed to return the completed diary card to the investigator at the next study visit.

- Collect and verify completed diary cards during discussion with the subject on Visit 2 (Month 1) and Visit 3 (Month 3).
- Any unreturned diary cards will be sought from the subject through telephone call(s) or any other convenient procedure.

The investigator will transcribe the collected information into the eCRF in English.

12.5.8.1. Time period for detecting and recording adverse events, serious adverse events and pregnancies (Amended, 23 November 2020)

All AEs during 30 days following administration of each dose of study vaccine (Day 1 to Day 30) must be recorded into the appropriate section of the eCRF, irrespective of intensity or whether or not they are considered vaccination-related.

The time period for collecting and recording *all* SAEs will begin at the first receipt of study vaccine and will end 12 months following administration of the last dose of study vaccine for each subject. See Section [12.5.9](#) for instructions on reporting of SAEs.

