
However, any SAEs assessed as related to study participation (e.g. study treatment, protocol-mandated procedures, invasive tests, or change in existing therapy) or related to a **GlaxoSmithKline** product will be recorded from the time a subject consent to participate in the study.

All AEs/SAEs leading to withdrawal from the study will be collected and recorded from the time of the first receipt of study vaccine.

SAEs that are related to the study vaccine will be collected and recorded from the time of the first receipt of study vaccine until the subject is discharged from the study.

In addition to the above-mentioned reporting requirements and in order to fulfil international reporting obligations, SAEs that are related to study participation (i.e. protocol-mandated procedures, invasive tests, a change from existing therapy) or are related to a concurrent **GlaxoSmithKline** medication/vaccine will be collected and recorded from the time the subject consents to participate in the study until she/he is discharged from the study.

The time period for collecting and recording pregnancies will begin at the first receipt of study vaccine until study end. See section [12.5.9](#) for instructions on reporting of pregnancies. This applies to pregnancy cases with exposure to **the study treatment** at any age of gestation. The timing of exposure to **the study treatment** during pregnancy is estimated in relation to the first day of the last menstrual period, ultrasound or known date of fertilization (e.g., assisted reproductive technology).

The time period for collecting and recording of pIMDs will begin at the first receipt of study vaccine and will end 12 months following administration of the last dose of study vaccine. ***Beyond this time period, only serious pIMDs that are related to the study vaccine are to be reported.*** See section [12.5.9.5](#) for instructions on reporting of pIMDs. ***(Amended, 23 November 2020)***

12.5.8.2. Evaluation of adverse events and serious adverse events**12.5.8.2.1. Active questioning to detect adverse events and serious adverse events**

As a consistent method of collecting AEs, the subject/subject's LAR(s) should be asked a non-leading question such as:

'Have you felt different in any way since receiving the vaccine or since the previous visit?'

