5.7.2. Additional considerations

The table on solicited local and general AEs will be presented separately according to GSK grading and grading scale provided by Chinese authorities.

Duration of each solicited local and general AE during the solicited follow-up period will be presented. Total duration of each individual solicited local and general AE will be tabulated.

Duration of each grade 3 solicited local and general AE during the solicited follow-up period will be presented in the table by GSK grading. Duration of each grade 3 and above solicited local and general AE during the solicited follow-up period will be presented in the table by Chinese authority grading.

Listing of complication related to confirmed HZ episode will be presented.

Number and percentage of subjects experiencing fatal SAEs, classified by MedDRA Primary System Organ Class and Preferred Term will be tabulated using date of onset of SAE from study start up to study end will be presented with 95% CI for web disclosure.

The table for web disclosure related to ***solicited adverse events*** endpoint will be based on both GSK and Chinese intensity scale.

Summary of subjects with serious adverse events related to study participation and not by the study vaccines or to GlaxoSmithKline concomitant medication/vaccine during the entire study period based on ES.

Following listings of concomitant medications related to confirmed HZ episode will be presented based on Exposed Set:

- ***Pain rescue medication to control HZ pain***
- ***Antiviral treatment for HZ***
- ***Other therapy for HZ***

Additional analyses/considerations due to COVID-19 pandemic on ES:

- ***Summary of COVID-19 Assessment.***
- ***Incidence of COVID-19 as an AE and SAE. A standardized MedDRA Query (SMQ) will be used to identify all COVID-19 cases reported as AEs.***
- ***A column to identify COVID-19 AEs/SAEs will be added to listing of (S)AEs and solicited adverse events leading to study or treatment discontinuation from first vaccination up to study end.***

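### The all-cause fatal SAE table to study end covers a period after month 12 post-dose in which the protocol does not clearly require unrelated deaths to be recorded

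*SAP*

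**What the plan says.** **Analysis.** SAP 5.7.2 adds a table of subjects with fatal SAEs by system organ class and preferred term, "tabulated using date of onset of SAE from study start up to study end", with a 95% CI and for web disclosure. It sets no causality limit. Protocol 10.3.5 plans the same table for three windows, the last two being "first vaccination up to 12 months post last vaccination and from study start up to study end will be presented with 95% CI". SAP 5.7.1 keeps only the 30-day and 12-month windows for any-cause fatal SAEs and takes only related fatal SAEs to study end. SAP section 8 drops tabulation by date of death, so onset date governs.

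**Endpoint.** Protocol Table 7 lists any-cause fatal SAEs to 30 days and to 12 months after the last vaccination. Its study-end endpoint is narrower: "Occurrence of related-fatal SAEs from Day 1 up to end of study".

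**Collection.** Under protocol 12.5.8.1, the period for all SAEs "will end 12 months following administration of the last dose of study vaccine for each subject". Table 19 footnote b in 8.5.2 adds: "Beyond this time period, only related SAEs (including related serious pIMDs as per investigator assessment) are to be reported". A separate rule in 12.5.8.1 reads: "All AEs/SAEs leading to withdrawal from the study will be collected and recorded from the time of the first receipt of study vaccine". That rule has no 12-month stop and no causality condition.

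**The concern.** One table reports deaths of any cause over a window whose last part has no clear instruction to collect them. If a site treats the 12-month stop as the operative rule, an unrelated death in month 15 after the last dose is not reported as an SAE. If it treats the death as an SAE leading to withdrawal, it is.

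Nothing in the planned table would show the difference. SAP 9.2.3 counts every vaccinated subject and treats those with no reported event as event-free, so an uncaptured death becomes a subject without a fatal SAE. Someone reading the posted result would take it as deaths of any cause to study end, with a confidence interval, although completeness may change partway through. This is the one fatal SAE table in the SAP that departs from the pattern of any cause to 12 months and related only thereafter.

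**Working it through.** There is no stated figure to reproduce. The check sets the rules side by side, asks whether the late period exists, and then looks at scale.

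**1. The same late unrelated fatal SAE under each passage**

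| Passage | Rule for onset more than 12 months after last dose | Unrelated death captured? |
|---|---|---|
| Protocol 12.5.8.1, all SAEs | Collection has ended | No |
| Protocol Table 19, footnote b (pIMD row) | Related SAEs only | No |
| Protocol 12.5.8.1, SAEs related to the vaccine, to study participation or to a concurrent sponsor product | Collected until discharge | No |
| Protocol 12.5.8.1, events leading to withdrawal | No stop date, no causality limit | Yes, if a death counts as a withdrawal |
| Schedule of Activities, withdrawal row | Marked at monthly contacts to study end | Same condition |
| Schedule of Activities, row for SAEs, pIMDs and pregnancies | Marked at monthly contacts, no 12-month limit shown; refers to 12.5.8 | Unclear |
| Protocol 10.3.5 and SAP 5.7.2 tables | Any cause to study end | Presupposed |

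Whether a death counts as a withdrawal depends on protocol 9.1. It defines withdrawal as being unavailable for the concluding contact, which literally includes a subject who has died. Death is not among the listed reasons. The nearest is an AE requiring expedited reporting, but 12.5.9.1 ties prompt SAE reporting to the periods in 12.5.8, which leads back to the same question.

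The period bars of Table 19 are not visible in the extracted text, so nothing here relies on them.

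**2. The late period exists by design**

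Inputs: the first-visit dates in SAP 9.2.3 run from 14 May 2021 to 15 September 2021, a gap of 124 days. Study conclusion is about 430 days after the last subject's enrolment (protocol 5.2). The dose interval is 60 days (Table 5), and the all-SAE window is 365 days after the last dose.

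- The last subject enrolled on or after 15 September 2021, so projected conclusion is no earlier than 15 September 2021 + 430 days = 19 November 2022.
- The first subject leaves the all-SAE window at 14 May 2021 + 60 + 365 days = 13 July 2022.
- Minimum late follow-up for that subject is 124 + 430 − 60 − 365 = 129 days, or 129 − 30 = 99 days if the concluding contact falls 30 days before the projected date.

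This is the longest-followed subject, so it shows that the period exists and is not an average. If follow-up is extended to reach 27 cases (protocol 10.1.2, SAP 7.1), every subject still followed enters the late period.

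**3. Scale, under assumptions only**

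The documents give neither mortality nor mean late follow-up. Take 95% of 6138 subjects still followed (using the 5% drop-out assumption in protocol 10.1.2), an assumed mean late follow-up of 2 to 6 months, and an assumed mortality of 2 to 10 per 1000 person-years:

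- Low: 6138 × 0.95 × (2/12) × 0.002 = 1.9
- High: 6138 × 0.95 × (6/12) × 0.010 = 29.2

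That is roughly 2 to 29 deaths over both arms in the period where the rule is unclear. It is not an estimate of deaths missed, and it counts by time of death, whereas the table uses SAE onset.

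**The case against.** The strongest reply is that a route for late deaths already exists. Events leading to withdrawal are recorded from first dose whatever their cause, the Schedule of Activities carries this to study end, and 9.1 defines withdrawal broadly enough to include death. Footnote b sits on the pIMD row and cannot be the complete rule, because 12.5.8.1 also collects SAEs related to study participation or to a concurrent sponsor product until discharge. Moreover, 12.5.8.1 does not itself say that only related SAEs are reported after 12 months; its sentence of that kind concerns serious pIMDs. The affected table is descriptive and was added for web disclosure.

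Most of this stands. A reader might infer that the protocol bars reporting of late unrelated deaths, so that the posted table necessarily understates mortality in both arms. The documents do not support that: undercounting is possible but not shown. Nor does the shortfall reach back before month 12, because SAEs are followed to outcome (8.5.5) and an event with earlier onset that later proves fatal is counted.

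What the reply does not supply is a passage saying that a death is to be recorded as an SAE leading to withdrawal. Two stated rules still give different answers for the same death, and the completeness of the table depends on which one a site follows.

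**Conclusion.** The mismatch holds as a risk of site-dependent capture. The posted table can understate fatal SAEs with onset more than 12 months after the last dose; the documents do not establish that it does, or by how many. The figures of 2 to 29 deaths rest on assumed mortality and follow-up and mark only what is exposed to the ambiguity.

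The collection rules are the same in both blinded arms, so there is no ground to infer a bias between arms. Primary efficacy and the 30-day and 12-month fatal SAE tables are unaffected. The point is still worth acting on, because this is the publicly posted any-cause figure and the correction is cheap.

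**What to change.** **Preferred.** Reconcile protocol 12.5.8.1, Table 19 footnote b and the withdrawal rule with one sentence: every death is recorded as a fatal SAE until study conclusion, whatever its relationship to vaccination. Monthly contacts already run to study end, so the cost is a few more SAE forms.

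**If collection can no longer be changed.** This may be the position, since SAP Amendment 1 is dated 10 May 2023. Keep every recorded death in the posted table and add a footnote saying that systematic all-cause collection ended 12 months after the last vaccination, and that later events are those judged related or recorded as leading to withdrawal. The cost is one footnote.

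Do not resolve the mismatch by restricting the table to related deaths. That would discard late unrelated deaths already recorded under the withdrawal rule and make the posted figure less complete.

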6. ANALYSIS INTERPRETATION

The primary objective of VE in the prevention of HZ compared to placebo in Chinese adults \geq 50 YOA, as measured by the reduction in HZ risk is considered met if the LL of the 2-sided 95% CI of VE is above 25%.

For all secondary objectives, analyses will be descriptive with the aim to characterize the differences in reactogenicity, safety and immunogenicity between groups.

7. INTERIM ANALYSES

7.1. Sequence of analyses

The analysis of all primary and secondary endpoints will be performed when all data up to study conclusion are available. A clinical study report (CSR) will be written at this stage and individual listings will be included.

One final analysis is planned and will be triggered when the following will take place:

- When at least 27 confirmed cases of HZ have accrued in the primary cohort for efficacy (cut-off date for primary efficacy analysis); AND
- When all subjects have completed at least 12 months safety follow-up post last vaccination.

Data contributing to the analysis of the primary efficacy objective (confirmed HZ cases) will be collected until the cut-off date. After the cut-off date, case confirmation of any new suspected HZ will not be performed. Once the study reaches the cut-off date, the conclusion contact for a subject will be planned based on the status of the safety follow-up:

- **Cut-off date reached before the completion of safety follow-up** – Continue the monthly safety follow-up after the cut-off date until all subjects have completed 12 months of follow-up post last dose.
- **Cut-off date reached after the completion of safety follow-up** – Continue the monthly contacts after the completion of the 12 months safety follow-up period until at least 27 confirmed HZ cases have accrued (cut-off date).

When the trigger for primary efficacy analysis is reached, subjects with an ongoing HZ episode will be followed until Day HZ-29.

The conclusion contact of the last subject will be the study end.

If the data for exploratory endpoints become available at a later stage, (an) additional analysis/ analyses will be performed. These analyses will be documented in the annex study report.

Description	Disclosure Purpose (CTRS=public posting, SR=Study report, internal)
Final	Public disclosure, Study report

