5.5.1. Analysis of efficacy planned in the protocol

5.5.1.1. Primary Objective

The primary inferential analysis of efficacy on the mES will be based on the occurrence of the primary endpoint anytime from 30 days after the administration of the second dose of the study vaccine up to study end. All subjects from the mES will contribute to the comparison.

It will consider the exact inference on the relative risk (RR) adjusted for age strata conditionally to the total number of HZ cases observed and time at risk. This method computes an exact CI around the rate ratio (ratio of the event rates in the RZV group versus control group) and takes into account, the sum of the time at risk of the subjects within each group.

Incidence rate and VE with 95% CI will be calculated using Poisson method. The VE will be defined as 1 minus the RR. RR is defined as the ratio of the incidence rates of the RZV group over the placebo group [VE= (1 – RR) x 100]

The VE of RZV against HZ will be demonstrated if the LL of the two-sided 95% CI of VE is above 25%. All p-values reported will be related to the null hypothesis test $VE = 0$.

The calculation of the time at risk and other statistical method detail are provided in Section 9.2.1.

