5.5.2. Additional considerations

Following descriptive table and figure will be generated by study groups on mES and ES:

- For each study group, the number of subjects at risk, person-year, number and incidence of confirmed HZ will be tabulated overall.
- Forest plot for vaccine efficacy against HZ by age strata and overall during the entire study period
- ***Cumulative incidence curve for HZ for each study group.***
- Number and percentage of episodes of all confirmed HZ episodes during the entire study period.
- Number and percentage of confirmed HZ episodes out of all the suspected cases reported.
- Number and percentage of suspected cases for which at least one PCR sample was collected on ES only.
- Distribution of suspected HZ cases using the HZ classification tools (PCR testing & HZ Ascertainment Committee (HZAC))
- The vaccine efficacy will be assessed by Poisson method for primary objective and fitted via the PROC GENMOD procedure according to the following code

```
PROC GENMOD DATA=pois_ve EXACTONLY;  
BY AGECAT;  
STRATA AGECAT;  
CLASS AGECAT/PARAM=ref;  
MODEL nb_cases = group_nb/DIST=poisson OFFSET = Log_T LINK=log;  
EXACT group_nb /ESTIMATE OUTDIST=dist ALPHA=0.05;  
ODS OUTPUT ExactParmEst=estimate ExactTests=ExactTest;  
RUN;
```

Where,

nb_case = number of cases

[figure not shown]
agecat = Age strata categories (50-69 and \geq 70 YOA)

group_nb = Group information of the subject (treatment received by subject)

Log_T = Log of the follow-up time

```
DATA VE ;  
SET ESTIMATE;  
FORMAT VE best12. ll best12. ul best12.;  
VE = ( 1 - exp (estimate)) * 100;  
ll = ( 1 - exp (UPPERCL)) * 100;  
ul = ( 1 - exp (LOWERCL)) * 100;  
RUN;
```

CCI

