9.2.1. HZ incidence

- For the primary analysis of HZ incidence, first confirmed HZ episode will be considered.
- The HZ onset date is the earlier of the following two events: 1) the HZ rash start date; or 2) the date on which pain/itching or abnormal sensation at the site of a subsequent HZ rash is first noted.
- A suspected case of HZ can be confirmed by GSK in two ways:
 - **By PCR:** Rash lesion samples will be collected from subjects clinically diagnosed as having a suspected case of HZ. The samples will be transferred to GSK or a validated laboratory designated by GSK Biologicals and analyzed using standardized and validated procedures for laboratory diagnosis of HZ by PCR (see Section 12.2 of the protocol).
 - **By the HZ Ascertainment Committee (HZAC):** All suspected HZ cases will be referred to the HZAC. The HZAC will classify all referred cases as either “HZ” or “not HZ” or “not able to decide” (see Section 12.2 of the protocol). The HZAC classification will serve as the final case definition only when the case cannot be confirmed or excluded by PCR. Therefore, definitive PCR results, when available, will determine the final HZ case assignment. In such cases, the HZAC classification will not contribute to HZ case determination decision
- For a given subject and for HZ episode, missing or non-evaluable measurements will not be imputed for the primary analysis. The missing endpoint and censoring are considered to occur independently, and the pattern being either Missing Completely At Random (MCAR) or Missing At Random (MAR) only.
- For HZ analysis, due to the algorithm used and taking into account both laboratory and HZAC results, no imputation and no sensitivity analysis for missing data will be performed.
- The “follow-up time at risk” for confirmed HZ is expressed in days and is computed according to the following rules:
 - The start date of the follow-up time (start) will be computed as follows:
 - From the dose 1 administration date for the analysis on the ES;
 - From 30 days post-dose 2 date for the analysis on the mES.
 - The end date of the follow-up time (stop) will be computed as follows:
 - Date of the last visit/contact for subjects who did not have an event;
 - Last contact date for subjects dropped out of the study, if not preceded by an event;

- Date of the event
- Date of HZ and/or VZV vaccination outside the study, if not preceded by an event
- The follow-up time at risk is computed using the following formula:

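### SAP 9.2.1 keeps counting time at risk after SAP 7.1 has stopped confirming cases at the 27-case cut-off, so descriptive HZ incidence can be understated; vaccine efficacy is barely affected

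*SAP*

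**What the plan says.** SAP 7.1 triggers the final analysis when two conditions are both met: at least 27 confirmed HZ cases in the primary efficacy cohort, which it calls the cut-off date, and 12 months of safety follow-up for everyone. Data for the primary efficacy objective are collected only to the cut-off. Then: "After the cut-off date, case confirmation of any new suspected HZ will not be performed".

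If the cut-off is reached before safety follow-up is complete, the instruction is: "Continue the monthly safety follow-up after the cut-off date until all subjects have completed 12 months of follow-up post last dose". The section adds: "The conclusion contact of the last subject will be the study end". In that branch study end is therefore later than the cut-off.

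Other parts of the SAP do not carry the cut-off:
- Section 9.2.1 stops time at risk at the event, drop-out, outside HZ or VZV vaccination, or "Date of the last visit/contact for subjects who did not have an event". It also says: "All suspected HZ cases will be referred to the HZAC".
- Section 5.5.1.1 bases the primary analysis on cases occurring "anytime from 30 days after the administration of the second dose of the study vaccine up to study end".
- Section 5.5.2 plans a "Forest plot for vaccine efficacy against HZ by age strata and overall during the entire study period", a cumulative incidence curve, and "Number and percentage of confirmed HZ episodes out of all the suspected cases reported".

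In the protocol, 10.1.2 makes 27 cases a minimum and also requires follow-up until the last enrolled subject has 12 months after the last vaccination. The primary analysis in 10.3.3 runs to study end. Section 10.3.3.1 limits person-years by an analysis cut-off date that it does not define, and its own stop-date list has no cut-off.

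**The concern.** A rate needs its numerator and denominator to cover the same period. Under 7.1 no case arising after the cut-off can be confirmed. Under 9.2.1 event-free subjects go on contributing time until their last contact. Where the cut-off precedes study end, the extra time lowers the incidence rate in both arms and flattens the late part of the cumulative incidence curves. The share of suspected episodes that are confirmed is also diluted, because suspected cases after the cut-off enter its denominator and cannot enter its numerator.

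These are descriptive outputs, but incidence by arm is a planned result and the final analysis feeds the study report and public disclosure. The cut-off is also not defined to the day: it could be the onset of the 27th case or the date its confirmation is recorded. Nor does the SAP say what happens to suspected cases still pending then. Two programmers could arrive at different case counts.

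**Working it through.** **1. The plan's own figures.** From protocol 10.1 and 10.1.2: 2762 evaluable per group, placebo rate 0.85% per year, VE 85%, success bound 25%, one-sided alpha 2.5%, 10% non-evaluable.
- Placebo cases in one year: 2762 × 0.0085 = 23.5. RZV: 23.5 × 0.15 = 3.5. Total 27.0, as planned.
- The RZV share of cases is 0.75/1.75 = 0.4286 at the null and 0.15/1.15 = 0.1304 under the alternative. With 27 cases the exact test rejects at 6 or fewer RZV cases: alpha 0.0216, power 94.7%, consistent with at least 90%.
- Enrolled: 5524/0.9 = 6138.

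**2. Cases expected by the end of safety follow-up.** Assume uniform enrolment over E months. Time at risk in the mES starts at about Month 3, and study end is E + 14 months from first enrolment, so mean time at risk is 11 + E/2 months.

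Expected cases = 2762 × 0.0085 × 1.15 × (11 + E/2)/12
- E = 4: 27.0 × 13/12 = 29.2
- E = 6: 27.0 × 14/12 = 31.5

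The documents do not give E. The first-subject dates by centre in SAP 9.2.3 run from 14 May to 15 September 2021, so about 4 months is a floor. Six months is an assumption.

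**3. Understatement at expected counts.** Let L be the months from onset of the 27th case to the cut-off (also an assumption). Cases accrue at 27.0/12 = 2.25 per month.

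Understatement = max(0, 1 − (27 + 2.25 L)/expected cases)

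| | L = 0 | L = 1 | L = 2 |
|---|---|---|---|
| E = 4 | 8% | 0% | 0% |
| E = 6 | 14% | 7% | 0% |

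With L = 0, the planning rate of 8.5 per 1000 person-years would be reported as 7.85 (E = 4) or 7.29 (E = 6). For wider E at L = 0, the understatement is 4% at 3 months, 23% at 9 and 29% at 12.

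**4. Placebo rate below which no effect is expected.** Rate = 27 / [2762 × 1.15 × (11 + E/2 − L)/12]. For L = 0/1/2 this is 0.78/0.85/0.93% per year (E = 4) and 0.73/0.78/0.85% (E = 6). Protocol 3.2 gives 3.2 to 8.6 per 1000 person-years, so most of that range lies below these values.

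**5. Random case timing.** Simulation of 6000 trials per setting, with exponential onset and no further drop-out. Values are for L = 0/1/2; the mean counts zero when the cut-off is not early.

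| Placebo rate | E | Cut-off early | Mean understatement |
|---|---|---|---|
| 0.85%/yr | 4 | 67/52/34% | 12/7/4% |
| 0.85%/yr | 6 | 80/67/52% | 16/11/6.5% |
| 0.6%/yr | 4 | 11/5/2% | under 2% |
| 0.6%/yr | 6 | 18/10/5% | under 2% |

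**6. Effect on VE.** Take 4 RZV and 23 placebo cases, one year at risk, and half a year for each case.
- To the cut-off: T(RZV) = 2758 + 2 = 2760 and T(placebo) = 2739 + 11.5 = 2750.5. VE = 1 − (4/2760)/(23/2750.5) = 82.67%, exact 95% CI 49.28 to 95.64.
- With 3 further months: T(RZV) = 2760 + 2758/4 = 3449.5 and T(placebo) = 2750.5 + 2739/4 = 3435.25. VE = 82.68%, CI 49.31 to 95.65.

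Placebo incidence falls from 8.36 to 6.70 per 1000 person-years, yet the placebo-to-RZV time ratio only moves from 0.9966 to 0.9959, so the dilution cancels in the rate ratio. If placebo lost 10% of its person-time in those 3 months, VE would be 83.0% with lower limit 50.3%. In the simulation the lower limit moved by at most 0.65 points (99th percentile 0.26 or less), and the 25% decision never differed. The intervals here are unstratified; the SAP adjusts for age stratum.

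**The case against.** The strongest reply is that 9.2.1 and 5.5.1.1 follow the protocol and 7.1 is the outlier. That stands. The stop-date list and the study-end window both come from the protocol, where 27 cases is a floor that can extend follow-up.

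A reader might infer from the person-years sentence in protocol 10.3.3.1 that the protocol already truncates at the 27th case and that 9.2.1 contradicts it. The documents do not support this. That sentence names only an analysis cut-off, and only SAP 7.1 ties a cut-off to 27 cases.

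A reader might also see a conflict with protocol 8.3.1.1, which has HZ cases reported until study end. There is none: 7.1 stops confirmation, not recording, and SAP 5.7.1 still lists every suspected episode. The general sentence on referral to the ascertainment committee can be read as qualified by 7.1, though saying so would help.

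It can be argued that 7.1 already limits person-time, since data contributing to the primary objective stop at the cut-off. But its parenthesis names only confirmed cases, and 9.2.1 is the explicit derivation rule.

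Finally, the early-cut-off branch may not occur, and accrual of confirmed cases implies some lag, which shrinks the effect. Both are true and limit its size.

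**Conclusion.** The mismatch within the SAP is real and minor. Following 7.1 and 9.2.1 literally gives a wrong incidence rate whenever the cut-off precedes the end of follow-up. The size depends on enrolment duration and lag, neither of which is in the documents. Near the planning rate it ranges from nothing to low double digits in percent; lower in the protocol's incidence range, little or nothing is expected. The dilution of the confirmed-to-suspected percentage was not quantified.

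A reader might infer that the primary result is at risk. It is not: the dilution is nearly the same in both arms, and the lower limit shifts by under about 1 point.

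The departure from the protocol lies in 7.1, and no visible item in SAP section 8 declares it. One item there is redacted and table layouts are in a separate document (SAP 10.2), so it may be handled where it cannot be seen.

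**What to change.** Make SAP 7.1 and 9.2.1 use the same end date. Either route works.

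**Keep the stop in 7.1.**
- Add the efficacy cut-off date, if earlier, to the 9.2.1 stop dates.
- Define that date exactly: onset of the 27th confirmed mES case, or the date its confirmation is recorded.
- State that suspected cases with onset on or before it are still confirmed.
- Use the same date in 5.5.1.1, in the 5.5.2 efficacy outputs and in the suspected-case denominator, and qualify the committee-referral sentence in 9.2.1.
- List both the stop in confirmation and the shortened primary window in SAP section 8 as changes from the protocol.

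The cost is wording and one extra term in a derivation, with no new data, no extra laboratory or committee work, and no effect on sample size.

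**Or confirm cases to study end**, as the protocol's primary window implies, and amend 7.1. The 9.2.1 stop dates and the windows in 5.5.1.1 and 5.5.2 then stand. This needs some further PCR testing and committee review for cases after the 27th.
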